### **Progress Report (Quarterly)**

Research staff will generate three quarterly study reports per year that outline study progress including recruitment, retention/attrition, any protocol deviation or violation that warrants a note-to-file, and AEs, SAEs, and unanticipated problems for that particular quarter. This report will be provided to the Co-PIs and the Chair of the DSMC. The Chair of the DSMC may solicit input from the other DSMC members if she detects anything of concern (e.g., higher rates of AEs than anticipated). The Chair of the DSMC will generate a report only if there is anything of concern that will be supplied to the study PIs, the UW IRB, and NCCIH.

### **Annual Report**

Study staff will generate an Annual Report during the last quarter of the year. The structure of the annual report will be identical to the three quarterly reports done earlier in the year; that is, it will follow the Study Report Outline (see below) with a general summary of what has occurred over the past year and most recent updates and progress since the third quarterly report. It will also include a list and summary of any protocol deviation or violation that warrants a note-to-file, and AEs, SAEs, and unanticipated problems; anything already reviewed in previous quarters by the DSMC Chair and Co-PIs will be clearly indicated in the report. In addition, the Annual Report will address (1) whether AE rates are consistent with pre-study assumptions; (2) reason for dropouts from the study; (3) whether all participants met entry criteria; (4) whether continuation of the study is justified on the basis that additional data are needed to accomplish the stated aims of the study; and (5) conditions whereby the study might be terminated prematurely. The Annual Report will be sent to all members of the DSMC. The DSMC along with the co-PIs will convene to review and discuss the report. The annual progress report will be forwarded to (1) the UW IRB and (2) NCCIH.

### **Study Report Outline for the Independent Monitor(s) (Interim or Annual Reports)**

The study team will generate progress reports on a quarterly basis (three per year) for review by the Chair of the DSMC, as well as an annual report (during the final quarter of the year) to be reviewed by all DSMC members. There will be a total of four reports (three quarterly, one annual) per calendar year.

**Study Report Outline**

- I. Table of Contents
- II. Introduction
  - a. Summary of Study Status and Issues or Problems
- III. Study Administration
  - a. Recruitment Status
    - i. Overall Recruitment Status and Recruitment Source
    - ii. Comparison of Targeted to Actual Enrollment
    - iii. Reasons for Ineligibility
    - iv. Reasons for Declination, Unable to Contact, Deferral
- IV. Study Data Reports/Tables or Figures
  - a. General Information
    - i. Enrollment Status
    - ii. Demographic/Baseline Data
    - iii. Assessment Retention
    - iv. Treatment Participation
    - v. Treatment Fidelity
- V. Safety Assessment
  - a. SAEs
  - b. Adverse Events
  - c. Reportable Problems
  - d. Protocol Deviations

Study Report tables will be generated only from aggregate (not by group assignment) baseline and aggregate safety data for the study population.

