### **F3. Reporting Procedures**

#### **F3a. Regulatory Event Documentation**

All regulatory events, incidents, or problems involving risks to participants, including AEs, SAEs, and Unanticipated Problems (UP), will be documented in the REDCap electronic database that houses all study data. All regulatory events will share a common electronic form template. Two separate copies of the same form will exist, (1) one for events involving information that could unblind staff to a participant's treatment allocation, and (2) another for events without details that could unblind staff to a participant's treatment allocation. Only unblinded staff will have access to the form that outlines events with details that could unblind staff to a participant's treatment intervention. The form will be filled out for every regulatory event. A study clinician will review all events that are designated AEs or SAEs to assess severity and relationship to study procedures.

The Regulatory Event form will assess the following information for all three event types (AE, SAE, and UP):

- A brief description of the incident/problem.
- Dates corresponding to event onset, stop, and location.
- Whether or not the event was unexpected or unanticipated.
- Whether or not the event placed participants or others at greater risk of harm than was previously recognized.
- The degree to which the event was related to study procedures.
- Whether or not the study procedures were discontinued due to the event.
- The steps taken to remedy the event.
- The steps taken to report the event to the appropriate entities.
- (AE/SAE only) A ranking of the severity of the event according to section F2c.
- (AE/SAE only) The specific outcome of the event.
- (SAE only) The category of the SAE.

For reporting purposes, regulatory event documentation will be aggregated into central reports using REDCap's "Reports" functionality. The "Reports" functionality allows data to be pulled from the Regulatory Event forms and summarized in one central report. The content of these reports and the frequency in which they are distributed to regulatory bodies is outlined in sections F3b. and F3c.

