#### **F3b. AE Reporting**

Research staff will generate reports summarizing all AEs for each participant using the REDCap “Report” feature outlined above in section F3a. The report will contain the participant’s code number, date of AE, severity, attribution level to study, action taken, and outcome. These adverse events will be provided quarterly in this format to the DSMC, UW IRB, and NCCIH in accordance with requirements.

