### **F3c. SAE/Unanticipated Problem Reporting**

- Unanticipated fatal or life-threatening SAEs at least possibly related to study procedures will be reported immediately to the NCCIH Program Officer, Chair of the DSMC, and the UW IRB.
- Breaches of confidentiality or inappropriate access to protected health information will be reported to the NCCIH Program Officer, Chair of the DSMC, and the UW IRB within 24 hours.
- Other unanticipated SAEs or serious problems at least possibly related to study procedures will be reported to the NCCIH Program Officer and DSMC Chair within 5 days, and to the UW IRB within 10 days.
- Anticipated or unrelated SAEs will be reported to the DSMC and NCCIH Program Officer as part of the annual DSM report.

Research staff will record all SAEs and unanticipated problems using the Regulatory Event form outlined above in section F3a. These serious adverse events/problems will be summarized using the REDCap “Report” format and provided quarterly in this format to the DSMC, the UW IRB, and NCCIH in accordance with requirements.

The Chair of the DSMC will be contacted when an SAE/unanticipated problem is discovered to receive consultation on the matter. The Chair of the DSMC will use her discretion to determine whether the other DSMC members should also provide additional consultation.

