#### **F4e. Stopping Rules**

This study will be stopped prior to its completion if: (1) one of the interventions is associated with adverse effects that call into question the safety of the intervention; (2) any new information becomes available during the trial that necessitates stopping the trial; or (3) other situations occur that might warrant stopping the trial.

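### The first stopping criterion concerns harm from a single intervention, but the reports described give the DSMC no safety comparison by arm

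*Protocol*

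**What the plan says.** Protocol F4e lists three grounds for stopping early. The first is that "one of the interventions is associated with adverse effects that call into question the safety of the intervention". It sets no threshold and does not say who applies it.

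Protocol F4g, Study Report Outline, fixes what the monitoring tables contain: "Study Report tables will be generated only from aggregate (not by group assignment) baseline and aggregate safety data for the study population". The outline serves three quarterly reports, which go to the co-PIs and the DSMC Chair, and one annual report, which goes to the whole DSMC. On the latter, F4g says: "The structure of the annual report will be identical to the three quarterly reports done earlier in the year". The annual report must also address "whether AE rates are consistent with pre-study assumptions", but no assumed rate is given.

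Three other routes carry safety information:

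- F3b sends the DSMC a quarterly listing for each participant, with code number, "date of AE, severity, attribution level to study, action taken, and outcome". F3c has SAEs and unanticipated problems summarized quarterly through the same REDCap report function.
- F3c adds contact for each event: "The Chair of the DSMC will be contacted when an SAE/unanticipated problem is discovered to receive consultation on the matter".
- F3a keeps two versions of the event form. "Only unblinded staff will have access to the form that outlines events with details that could unblind staff" to a participant's allocation.

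**The concern.** The criterion asks a question about one intervention. The tables meant to inform the monitor exclude, in express words, the variable needed to answer it. This is a stated restriction, not an omitted detail.

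It matters because the protocol itself foresees harms that differ by arm. E3b names physical strain or injury for activation skills, disorientation or grogginess for mindfulness meditation, and distressing memories for cognitive restructuring and mindfulness. E4b describes adverse-effect monitoring separately by intervention. Safety information is thus gathered with the arm in mind, and the arm is then dropped before the committee's tables are made. An excess confined to one arm would reach the committee mixed with the experience of the other two.

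**Working it through.** **Step 1. Each route to the DSMC, checked for arm.**

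| Route | Section | Arm shown? |
|---|---|---|
| Quarterly and annual report tables | F4g | No; excluded expressly |
| Quarterly AE listing by participant | F3b | Not a listed field |
| Quarterly SAE and unanticipated problem summaries | F3c | Not a listed field |
| Contact with the Chair for each SAE or unanticipated problem | F3c | Not stated |
| Event forms that could reveal allocation | F3a | Open to unblinded staff only; DSMC not named |

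No route in the available text gives the committee event counts by arm.

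**Step 2. What pooling does.** The documents state no AE rate, safety threshold or safety power, so there is no figure of the plan's own to reproduce. From the protocol: 3 arms and N = 90. Assumed: equal allocation, so 30 per arm. With background rate p0 in two arms and p1 in the third, the pooled rate is (2·p0 + p1)/3.

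- Doubling, p1 = 2·p0: pooled rate = 4·p0/3, a ratio of 1.33.
- Tripling, p1 = 3·p0: pooled rate = 5·p0/3, a ratio of 1.67.

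The excess is cut to one third. A pooled count of 15/90 is also the same whether the arms have 5, 5 and 5 events or 3, 3 and 9. That ambiguity remains at any sample size.

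**Step 3. Chance of a flag (illustration; all event rates assumed).** A flag is the smallest count whose one-sided exact binomial tail under p0 is at most 0.05 for the pooled 90, or at most 0.05/3 for a single arm of 30, which allows for looking at three arms. The pooled chance is P(X + Y ≥ threshold) with X ~ Bin(60, p0) and Y ~ Bin(30, p1). The arm's chance is P(Y ≥ threshold).

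| p0 | p1 | Pooled flag | Chance, pooled | Arm flag | Chance, harmed arm's own table |
|---|---|---|---|---|---|
| 5% | 10% | ≥9/90 | 0.14 | ≥5/30 | 0.18 |
| 5% | 15% | ≥9/90 | 0.33 | ≥5/30 | 0.48 |
| 10% | 20% | ≥15/90 | 0.21 | ≥8/30 | 0.24 |
| 10% | 30% | ≥15/90 | 0.55 | ≥8/30 | 0.72 |
| 20% | 40% | ≥25/90 | 0.44 | ≥12/30 | 0.57 |
| 20% | 60% | ≥25/90 | 0.91 | ≥12/30 | 0.99 |

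Counts are discrete, so the realised false-alarm rates are below 5% and not identical: 3.6%, 3.3% and 4.7% pooled, against 4.6%, 2.3% and 2.8% over three arms, for backgrounds of 5%, 10% and 20%.

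**The case against.** A reader might infer that the committee cannot see which arm carries a harm, or that the stopping criterion cannot be applied at all. The documents do not support either reading, for four reasons.

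- **Text not available.** The contents list places F4f, on designating a monitoring committee, between the stopping rules and the safety review plan. Its text was removed before this review, and a right of access to unblinded data could be set out there. The revision history (Version 2.2) also refers to a separate data and safety monitoring plan that is not among the documents. A provision in either cannot be excluded.
- **Not everything sent is pooled.** The F3b listing is by participant and carries an attribution to the study. A harm typical of one treatment, such as strain during assigned activity, could often be recognised from a single case.
- **People who know the arm can act.** F4e does not assign the rule to the DSMC, and F5 contemplates suspension by the IRB, the DSMC or an investigator. Both co-PIs are unblinded (table of blinded and unblinded staff in D6r) and review AEs quarterly (F4b). They also attend the annual review: "The DSMC along with the co-PIs will convene to review and discuss the report". Clinicians assess adverse effects in every arm (E4b).
- **The detection gain can be small.** For a doubling from a 5% or 10% background, the arm's own table adds about 0.03 to the chance of a flag. The table in the working also assumes full enrolment; interim counts would be smaller.

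All four stand as limits on the point. They do not remove it. If F4f grants access, it conflicts with the restriction to aggregate tables in F4g. Recognising single cases is not a comparison of rates, and it works least well for non-specific events. The co-PIs supervise the study clinicians and take part in analysis, so their knowledge does not replace independent review.

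**Conclusion.** The point holds in this form: the reports described in the available text give the DSMC no arm-level safety comparison, although the first stopping criterion is about one intervention. F4e and the Study Report Outline need to be reconciled.

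The failure to identify the arm follows from the text and needs no assumption about rates. The loss of detection is illustrative only. It rests on 30 per arm and assumed backgrounds of 5% to 20%, with a doubling or tripling in one arm. On those assumptions the chance of a flag is 0.14 to 0.91 pooled and 0.18 to 0.99 from the harmed arm's own table. The difference runs from about 0.03 (10% to 20%) to about 0.17 (10% to 30%). The treatments are described as carrying minimal risk, so this is a worthwhile repair to the monitoring plan and not evidence that participants are unprotected. Confidence in the wider claim about committee access is limited by the missing F4f.

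**What to change.** Reconcile F4e with the Study Report Outline in F4g, and check both against F4f. Keep the open report aggregate. Add a closed report, for DSMC members only, that tabulates AEs, SAEs and treatment withdrawals by coded arm (A/B/C). Unblinded staff would prepare it, and the code would be opened at the DSMC's request.

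Leave MME change out of the closed report. MME is the primary outcome (Table 3), and the SAP compares dose increase, decrease and no change between arms, so a tabulation by arm would be an unplanned interim look at that outcome.

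The cost is a short protocol amendment, one extra REDCap report and a closed portion of the annual DSMC meeting without the co-PIs. Allocation and events are already recorded in REDCap (D6k, F3a) and unblinded staff are in place (D6r). Blinded assessors stay blind because the closed report does not reach them.

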**F5. Reporting Changes in Study Status**

During the funding of this study, any action by the IRB, the DSMC, or one of the study investigators that results in a temporary or permanent suspension of the study will be reported to the NCCIH Program Officer within 1 business day of notification.

## **G. Potential Benefits of Research to Participants and Others**

Previous studies with the therapeutic skills taught in the planned study support their efficacy in reducing pain intensity and improving other pain-related outcomes. We anticipate based on this previous research that many of the participants will experience significant reductions in their daily pain intensity and opioid use and other benefits associated with the treatments. Participants in all three conditions will have the benefit of a caring and interested group leader, thus promoting therapeutic alliance, as well as interaction with other group members.

In our past research, many group members have expressed satisfaction from learning that there are other people with experiences similar to their own, and from receiving group treatment in a caring and nonjudgmental environment. Thus, participants in all three treatments will take away from the study new skills and knowledge regarding chronic pain and how to manage it, and – given previous results of RCTs for psychosocial interventions for chronic pain – should experience some degree of relief from pain and suffering and increases in their quality of life.

## **H. Publication of Research Findings**

Any manuscript will be made available for review by the study sponsor prior to submission.

## **I. Importance of Knowledge to Be Gained**

The findings from this study will provide clinically meaningful information that will have positive effects on the lives of patients with chronic pain who are at high risk for opioid misuse. The findings will provide important new information regarding for whom the three treatments studied are most beneficial for with respect to opioid use reduction. These moderation findings will inform the future development of patient-treatment matching algorithms. The results will also investigate the treatment mechanisms of the treatments studied, as well as those factors that underlie post-treatment relapse, maintenance, and continued gains following treatment. Results will elucidate the temporal sequence of lagged mechanism effects to determine rates of change in opioid use as a function of change in pain intensity and emotional distress. Results will also precisely inform relapse prevention interventions. Progress in the understanding of treatments has been hampered by the lack of mechanism studies, such as the one planned, to identify the mechanisms of treatment outcome and relapse. The current study will help address this significant gap.

## Appendix: Evaluation Timeline

Assessment	Screening	Enrollment	Pre-Treatment	Baseline Monitoring Period	Treatment & Treatment Monitoring Period	Post-Treatment Monitoring Period	Post-Treatment	3-Month Follow-up	6-Month Follow-up
Inclusion/Exclusion Criteria	X								
Informed Consent		X							
Baseline Data and Demographics		X							
Opioid Use MME (Re-Assessment of Study Eligibility)			X						
Opioid Use MME (Randomization Stratification)			X						
Opioid Use MME (Primary Outcome)			X	X	X	X	X	X	X
Secondary Outcomes			X	X	X	X	X	X	X
Primary Mechanisms			X	X	X	X	X	X	X
Secondary Mechanisms			X	X	X	X	X	X	X
Tertiary Outcomes			X				X	X	X
Tertiary Mechanisms			X				X	X	X
Moderators			X		X		X		
Treatment Homework Completion					X				
Participant Engagement					X				
Qualitative Outcomes							X		
Optional Assessments			X				X	X	X
Adverse Events	X	X	X	X	X	X	X	X	X

Mechanisms of Psychosocial Treatments on Opioid Use in Chronic Pain

Statistical Analysis Plan

Plan Date: July 23, 2024

IRB Title: Mechanisms of Psychosocial Treatments on Opioid Use in Chronic Pain

Short Title: Living in Full Even (LIFE) with Pain Study

NCT Number: NCT03916276

Mechanisms of Psychosocial Treatments on Opioid Use in Chronic Pain

A randomized, 3-group, parallel-design, 90-subject clinical trial to test the mediators and moderators of cognitive therapy, mindfulness meditation, and activation skills on individuals with heterogeneous chronic pain conditions who are at risk for opioid misuse.

Study Chairman or Principal Investigator:

[name]., Professor and Vice Chair for Research, University of Washington Department of Rehabilitation Medicine

[name]., Senior Lecturer, University of Queensland School of Psychology

Supported by:

The National Center of Complementary and Integrative Health (NCCIH)
3R01AT008559-02S1

Study Intervention Provided by:

University of Washington

Estimates of treatment effects on outcomes. Descriptive statistics were computed for all outcomes. At each follow-up time (post-treatment, 3- and 6-month follow-ups), the average daily medication in MME was categorized into three groups (increase in dose, decrease in dose, or no change in dose from pre-treatment to follow-up), and then calculated the proportion of individuals at each follow-up time that increased dose, decreased dose, or reported no change. We also calculated the 95% confidence interval (CI) for those proportions using Jeffreys method (Bayesian). We then compared these proportions between treatment conditions using a Chi-square test. We also calculated the difference in proportions (and 95% CI's) between each pair of interventions.

We calculated the mean and standard deviation of the change from pre-treatment to follow-up of all of the secondary outcomes, as well as their effect sizes (Cohen's d's) and 95% CI. We compared the mean changes of the interventions via an ANOVA (change in outcome as response and intervention group as a factor), and calculated between groups effects and 95% CI. Effect sizes were calculated using the macro effect size in R software.
